### *2.2a. Long Term Goal of Research*

Our ultimate goal is to conduct an RCT to answer the practical question of whether Tai Chi is effective for relieving cLBP in older adults **when added to** Usual Medical Care. Our Standard dose of Tai Chi would be 12-week 2x/weekly series of Tai Chi classes (see Section 5 for further details and justification). Because Tai Chi requires ongoing practice, maintaining the practice is critical and so we would investigate the value of including an Enhanced Tai Chi group that receives Standard Tai Chi plus a 24 week maintenance period of progressively fewer classes: 6 weeks of weekly classes, 6 weeks of every other week classes and 12 weeks of monthly classes). All classes would be 60 minutes long. Participants would be asked to practice 15 minutes at home on all non-class days. The anticipated design of our full-scale trial is depicted on the next page (note that Usual Medical Care will be available to all study groups). We are unclear regarding the value of an Attention Control, which will be included in one of the cohorts of the feasibility RCT:

[figure not shown]
Our principal hypotheses would be:

H1: Tai Chi is superior to Usual Medical Care at 12, 26, and 52 weeks. (Primary time point would be 12 weeks).

H2: Enhanced Tai Chi (standard + maintenance) is superior to Standard Tai Chi at 26 and 52 weeks. (Primary time point would be 52 weeks).

H3: Tai Chi is superior to Attention Control at 12, 26, and 52 weeks (assuming we include the AC group). (Primary time point would be 12 weeks).

The primary outcomes would be back-related dysfunction (most critical) and pain.

**Figure: Anticipated Design of Full-scale Trial**

### **3. STUDY DESIGN**

The feasibility study will be a three arm parallel group RCT comparing Enhanced Tai Chi to Comprehensive Health Education (Attention Control) to Usual Medical Care in older adults (65 years and older) with cLBP. We plan to recruit 78 community-dwelling, older adults from Kaiser Permanente Washington, an integrated healthcare system with a large population of Medicare enrollees and from the general population as necessary. We will randomize eligible and willing individuals in a 8:3:5 ratio to Enhanced Tai Chi (n=39), Attention Control (n=15) and Usual Medical Care (n=24) using a computer with a tamperproof program that is not predictable in advance. Participants in the Enhanced Tai Chi will receive 36 weeks of classes (which will be 60 minute classes for 2x/week for 12 weeks; followed by a maintenance schedule of 60 minutes classes 1x/week for 6 weeks, then 60 minute classes every 2 weeks for 6 weeks and then 60 minute classes every 4 weeks for 12 weeks. Participants will be asked to practice at home for 15 minutes on every non-class day. They will be provided with YouTube video access (and, if desired, DVDs), and handouts to assist with this.). All classes will be taught in a Kaiser Permanente Washington classroom. Data on adherence to Tai Chi classes and home practice will be collected during the classes themselves. Because Tai Chi will be taught as a series of progressive classes, participants will be recruited in two cohorts of 32 each; each class of Tai Chi will consist of 16 participants.

Outcome assessments will be collected at baseline, 12, 26, and 52 week during in-person visits. Outcome assessors will be unaware of any participant's study groups,

but participants will be asked to complete their own questionnaires. They will either complete them on paper forms or using a tablet computer designed to minimize errors.

This design will allow us to collect data on recruitment and randomization rates, acceptance and feasibility of the Tai Chi intervention (adherence to the standard and maintenance Tai Chi protocols), and follow-up rates, which are critical to assess feasibility of the full-scale RCT. By including these treatment groups – which represent the extremes in time commitment - in the feasibility RCT, we likely to collect data that is applicable to the other treatment groups (i.e., standard Tai Chi and Attention Control, if the latter is used) included in a full-scale RCT. At the 52 week follow-up, we will also obtain information from debriefing discussions with the study participants about aspects of the study that would require modification prior to the conduct of a larger RCT. We will use the proposed outcome measures and physical measures in their entirety to ensure that these are feasible in terms of participant burden. Because the RCT is underpowered for effectiveness, it is not appropriate to have specific hypotheses regarding effectiveness. Nonetheless, back-related function and pain would be the primary outcomes in the full-scale trial as described above.

## **4. SELECTION AND ENROLLMENT OF PARTICIPANTS**

### **4.1 Source of Participants**

Participants will be recruited from Kaiser Permanente Washington, an integrated health care system serving over 400,000 adult members in their primary care clinics in Washington State. This includes 67,341 members age 65+, of which over 10,000 made medical visits for back pain in 2014. This should provide an ample number of members who have chronic back pain who would be eligible for our study, particularly given our 2001 survey findings that 55% of older adults receiving care from GH reported they would be “very likely” to try “Tai Chi” for their back pain if their provider considered it a reasonable option and it was free. Furthermore, given the growing popularity of mind-body therapies in recent years since our 2001 survey, interest in Tai Chi has probably increased. Recruitment from the GH population will enhance the generalizability of our results to the large fraction of Americans that receive most of their medical care in primary care settings. We will augment the Kaiser Permanente Washington population as necessary by recruiting from the general Seattle area.

### **4.2 Inclusion Criteria**

Participants will need to meet all of the inclusion criteria to participate in the study. Participants must:

- Be men or women at least 65 years of age
- Have low back pain that has persisted for at least three months
- Have had back pain on at least half the days in the last 6 months
- Rate their low back pain at least 4 on a 0 to 10 back pain intensity scale
- Rate their activity limitations due to back pain at least 3 on a 0 to 10 scale
- Be members of Kaiser Permanente Washington integrative health care system or have a regular source of health care and health insurance
- Have normal cognition or only mild cognitive impairment ( score of <3 on 6 item Callahan screener)

- Be capable of understanding the study procedures and complying with them for the entire study period.
- Live close enough to the class site for attendance to be practical
- Give informed consent

Because there are a number of back pain diagnoses that might be given to eligible participants, we will cast a wide net using ICD9 or ICD10 codes that could be indicative of back pain without specific cause (i.e., ICD-10 codes: M54.5 Lumbago; M54.9 Backache; unspecified; M45.0 Other symptoms referable to back; S33.6XXA Sprains and strains, sacroiliac; S33.5XXA Sprains and strains, lumbar; S33.8XXA Sprains and strains, sacral; and S33.9XXA Sprains/ strains, unspecified site of back) or due to degenerative disease. Currently, ICD codes do not indicate whether the pain is chronic or not, so that must be determined by telephone interview. These are draft criteria and will be reviewed for completeness during the Administrative year of the grant.

#### **4.3 Exclusion Criteria**

Participants who have any of the exclusion criteria during screening or the baseline visit will be excluded from study participation. These exclusion criteria include:

- Specific conditions other than degenerative disease or spinal stenosis as cause of LBP (e.g., metastatic cancer, vertebral fracture, spinal infection, ankylosing spondylitis, spondylolisthesis).
- Prior lumbar spine surgery
- sciatica, or scheduled visits to a neurosurgeon or orthopedic surgeon.
- Receiving or seeking compensation for back pain
- Red flags of serious underlying illness (e.g., recent unexplained weight loss of 10 lbs or more, fever, recent increase in pain intensity)
- Have received Tai Chi training in the last 12 months or practiced yoga more than 5 times in that period. Other disabling conditions that might confound treatment effects (e.g., disabling heart or lung disease or diabetic neuropathy)
- Conditions making consent or treatment difficult (e.g., unwilling or unable to attend classes and practice at home, major psychoses, dementia, severe vision or hearing problems, lack of transportation, unable to read or speak English; cannot transfer weight from one leg to another or bend at the hips)
- Conditions making treatment unsafe or inappropriate (e.g., inability to stand independently, absolute contraindications to exercise such as uncontrolled arrhythmia, unstable angina, acute MI or CHF)
- Unwillingness to give informed consent

#### **4.4 Study Enrollment Procedures**

Our standard recruitment approach will be to use Kaiser Permanente Washington's electronic administrative and clinical databases to identify potentially eligible GH members who are at least 65 years of age with a visit to a health care provider that resulted in a diagnosis consistent with low back pain. We then mail invitation letters describing key eligibility requirements and describing logistical aspects of the trial to GH members at least 3 months after they have visited a GH provider for back pain. Individuals with interest in the study will be asked to either return a statement of interest or call our toll-free project number with their contact information. A

Research Specialist will then phone interested enrollees to answer questions, obtain oral consent for an initial telephone eligibility screen and determine preliminary eligibility using a computer program to guide the interviewer through a series of screening questions. The screening process will end with documentation in a database of either preliminary eligibility or ineligibility. Individuals whose responses suggest they are provisionally eligible and who interested in the feasibility RCT will then be scheduled to come to a group in-person assessment in a conference room at a large Kaiser Permanente Washington clinic. They will receive information about the details of the conference room location ahead of time. Individuals who were deemed provisionally eligible more than 10 days in advance of the scheduled baseline visit will be re-contacted by phone to make sure that their pain levels were sufficiently high that they remain eligible.

If necessary, we will explore two additional approaches: advertising in newsletters targeted at KP seniors (i.e., members of the KP Senior Caucus and mailings sent to Medicare recipients receiving care at KP) and through mailings to older adults meeting our eligibility criteria (based on data in the EMR) who have not recently visited their physician for back pain. It is likely that a substantial number of these older adults will have impairing cLBP but have given up on seeking medical care because it has not been effective or has had significant side effects.

In addition to inviting Kaiser Permanente Washington enrollees, we will also recruit participants from the general population of seniors in the Seattle-area. For general population recruitment, we will use a variety of recruitment methods such as radio ads, flyers on community bulletin boards, blogs, and direct mail postcards. If we are having trouble reaching seniors with chronic low back pain, we will enlist the help of our patient partners to help identify recruitment sources most relevant for the senior population. For the direct mail postcards, we will use a list service to purchase lists which include the name and addresses of people living within our recruitment area who are within the study age-range. People on the list will be sent a direct mail postcard which gives study information and directions for how to contact study staff if interested in participating. Once an interested person has contacted the study, the process will be the same as detailed above and the phone call will be analogous to returning the study postcard.

Those persons deemed preliminarily eligible will be scheduled to attend one of our in-person group eligibility screening and assessment visits at a Kaiser Permanente Washington Medical Center. While the in-person visits are in a group setting, physical assessments and randomization will take place in a private room adjacent to the group area. This method has worked well in other studies conducted by Drs. [name] and [name], but will be modified if suggested by the patient partners. During the group assessment visit, eligibility will be confirmed through completion of a final eligibility screening (e.g. demonstration of sufficient mobility, willingness to be randomized). If the participant is deemed eligible and is willing to participate, informed consent will be administered by a study Research Specialist. This will include an explanation of interview time commitments and content, intervention commitments (class attendance, home practice, and home practice diary completion), potential risks of participation,

potential benefits of participation, what to do for an adverse event, and options for discontinuation of participation in the study. The Research Specialist will also explain the handling of data and personal health information as dictated by HIPAA. After informed consent is obtained, the baseline questionnaire will be administered using either a study tablet computer or a paper questionnaire, whichever the participant prefers. The Research Specialist will be present and available to answer any questions that might arise while the participant is completing the baseline questionnaire. To ensure that all key outcome measures are collected at the baseline appointment, we will also have participants' complete physical assessments (Short Physical Performance Battery, Four Square Step Test, Gait Speed). Once the baseline questionnaire and physical assessments are complete, the Research Specialist will answer any remaining questions and randomize the participant to one of our study groups. Signed consent forms will be kept at the KPWHRI in a locked filing cabinet only accessible by the appropriate study staff.

Study staff will randomize each individual to their treatment group using a computer program, accessible by a laptop, designed to ensure that treatment allocation cannot be changed after randomization and cannot be viewed in advance. Our biostatistician will provide our study programmer with a computer-generated sequence of random numbers that will be then inserted into the computer program. Physical assessments and randomization will be carried out in a private space adjacent to the group visit room. Participants will be randomized in blocks of varying size to ensure balanced but unpredictable assignment of participants to both groups. Participants randomized to Tai Chi will be provided information about the time and location of the first class. This process, modified as necessary for older adults, will be repeated to assemble two consecutive recruitment cohorts of 32 participants. In the first cohort, 19 participants will be randomized to Enhanced Tai Chi protocol and 19 to Usual Medical Care. In the second cohort, 20 participants will be randomized to Enhanced Tai Chi protocol, 15 to the Comprehensive Health Education Classes (AC Group), and 5 to Usual Care. The advice from our patient partners, our team members with experience conducting studies of physical activity in older adults and the experience we gain enrolling participants in our small Tai Chi study this summer, will help ensure that our standard recruitment procedures are modified appropriately for this new study population. We will consider whether we should conduct randomization stratified by age (65-79; 80+) and gender because both are related to baseline measures of back dysfunction and pain.

In our large randomized trial of acupuncture for cLBP, we found no differences in the baseline characteristics of participants recruited through mailings and through advertisements in the health plan's quarterly magazine.

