## **iii. Preliminary Outcome Analyses**

Preliminary analyses will not be properly powered, but will alert us to potential analytic challenges in the full-scale trial. We will employ the analytic techniques we would propose in a full-scale trial. In our comparisons of treatments on the outcome measures, we will analyze outcomes from all follow-up time points in a single model, adjusting for possible correlation within individuals and treatment group cohorts using generalized estimating equations (GEE). Because we cannot reasonably make an assumption of constant or linear group differences over time, we will include an interaction term between treatment group and time point. We plan to adjust for baseline outcome value, gender, and age of analyses. The general form of the regression model will be:  $g(Y(t)) = \beta_0 + \beta_1 Baseline + \alpha_1 Trt + \alpha_2 Trt \times Time + \alpha_3 z + \varepsilon$ , where  $Y(t)$  is the response at follow-up time  $t$ , *Baseline* is the pre-randomization value of the outcome measure, *Trt* include a dummy variables for the Tai Chi group or the Comprehensive Health Education Control group, *Time* is a series of dummy variables indicating the follow-up times, and  $z$  is a vector of covariates representing other variables being adjusted for. (Note that  $\alpha_1$ ,  $\alpha_2$ , and  $\alpha_3$  are vectors.) The referent group in this model is the Usual Medical Care group. For binary and continuous outcomes, we will use appropriate link functions (i.e., logit for binary).

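### The stated 8:3:5 randomisation applies in neither cohort, and the preliminary outcome model has no cohort term in the mean

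*Protocol*

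**What the plan says.** Protocol Section 3 gives one ratio for the whole trial: "We will randomize eligible and willing individuals in a 8:3:5 ratio to Enhanced Tai Chi (n=39", with 15 to Attention Control (AC) and 24 to Usual Medical Care (UMC).

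Section 4.4 gives the allocation by cohort. "In the first cohort, 19 participants will be randomized to Enhanced Tai Chi protocol and 19 to Usual Medical Care". In the second cohort 20 go to Tai Chi (TC), "15 to the Comprehensive Health Education Classes (AC Group), and 5 to Usual Care". Section 2.2a agrees that AC is not in both cohorts, describing it as an arm "which will be included in one of the cohorts of the feasibility RCT". The timeline in Section 14 recruits the cohorts one after the other, in months 1-4 and 5-8.

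Section 4.4 also still speaks of "two consecutive recruitment cohorts of 32 participants", as does Section 3, whereas the Precis has cohorts of 38 and 40. Sections 4.4 and 9.2 describe blocked assignment to two groups in a three-arm trial.

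The outcome model is in Section 9.6 iii. On covariates it says "We plan to adjust for baseline outcome value, gender, and age of analyses". Cohort enters only through the correlation: "adjusting for possible correlation within individuals and treatment group cohorts using generalized estimating equations (GEE". "The referent group in this model is the Usual Medical Care group". The general form also carries a covariate vector z, with nothing named beyond gender and age. The SAP contains no outcome model and does not mention cohorts.

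**The concern.** There are two linked faults.

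First, Section 3 misdescribes the randomisation. Someone building the allocation list from it would put about 7 of the first 38 participants into AC, where Section 4.4 puts none.

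Second, arm is associated with cohort by design. Half of each cohort goes to TC, but the AC and UMC shares change sharply. Of the 24 UMC participants, 19 were randomised when AC was not an option. The model sets all 15 AC participants against all 24 UMC participants, without a cohort term in the mean. Any cohort difference left after baseline adjustment would then be mixed into the treatment contrasts, most of all AC against UMC.

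The documents give reasons why the cohorts could differ. They are consecutive, extra recruitment sources may be added as needed (Sections 4.1 and 4.4), Section 9.4 expects recruitment and follow-up procedures to be changed if they run into difficulty, and cohort 2 participants consent to a different set of arms.

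The outcome analyses are unpowered, but Section 9.6 iii says they use the techniques intended for the full-scale trial, and Section 2.2a leaves the value of an AC arm open.

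**Working it through.** **Inputs.** Cell sizes from Section 4.4: cohort 1 TC 19, UMC 19; cohort 2 TC 20, AC 15, UMC 5. Assumptions not in the documents: outcome SD 1, one time point, no dropout, independent observations, and a residual cohort shift d (cohort 2 minus cohort 1, after baseline adjustment) of 0.2 to 0.5 SD.

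**1. The stated ratio.** 78 × 8/16, 3/16, 5/16 = 39.0, 14.6, 24.4, which rounds to the stated 39, 15, 24. The cohort counts give the same totals: 19+20 = 39, 0+15 = 15, 19+5 = 24. So the totals agree. Applied within cohorts, however, 8:3:5 would give 19/7.1/11.9 of 38 and 20/7.5/12.5 of 40, against the planned 19/0/19 and 20/15/5.

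**2. Share of each arm from cohort 2.** TC 20/39 = 0.513; AC 15/15 = 1; UMC 5/24 = 0.208.

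**3. Bias without a cohort term.** Bias = (difference in cohort 2 share) × d. The factors are 0.513 − 0.208 = 0.304 (TC−UMC), 1 − 0.208 = 0.792 (AC−UMC) and 0.513 − 1 = −0.487 (TC−AC).

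**4. Standard errors.** Unadjusted information is n₁n₂/(n₁+n₂): 39×24/63 = 14.86, 15×24/39 = 9.23 and 39×15/54 = 10.83.

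With an additive cohort effect:
- TC−UMC: 19×19/38 + 20×5/25 = 9.5 + 4 = 13.50.
- AC−UMC: the cohort 2 UMC mean is estimated directly (variance 1/5) and indirectly through the other three TC and UMC cells (variance 1/20 + 1/19 + 1/19 = 0.155). Combined, the variance is 1/(5 + 6.44) = 0.0874. Adding 1/15 gives 0.154, information 6.49.
- TC−AC: in the same way, 1/(20 + 3.28) + 1/15 = 0.110, information 9.12.

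| Contrast | SE, no cohort | SE, with cohort | Information lost | SE, cohort 2 only |
|---|---|---|---|---|
| TC−UMC | 0.259 | 0.272 | 9% | – |
| AC−UMC | 0.329 | 0.393 | 30% | 0.516 (15×5/20 = 3.75) |
| TC−AC | 0.304 | 0.331 | 16% | 0.342 (20×15/35 = 8.57) |

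With the 10% loss assumed in Section 9.2, every SE is multiplied by 1/√0.9 = 1.054.

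**5. Coverage of a nominal 95% interval without the cohort term.** Φ(1.96 − b) − Φ(−1.96 − b), with b = |bias|/SE.

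| Contrast | Bias at d = 0.2 | Coverage | Bias at d = 0.5 | b | Coverage |
|---|---|---|---|---|---|
| TC−UMC | 0.06 | 94% | 0.15 | 0.59 | 91% |
| AC−UMC | 0.16 | 92% | 0.40 | 1.20 | 77% |
| TC−AC | −0.10 | 94% | −0.24 | 0.80 | 87% |

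**6. Does the planned GEE correlation remove it?** With exchangeable correlation inside the five arm-by-cohort cells (assumed intraclass correlation 0.01 to 0.05), the AC−UMC factor falls only from 0.79 to 0.77 and 0.71, while the SE rises to 0.352 and 0.429. At d = 0.5, b = 0.385/0.352 = 1.09 and 0.353/0.429 = 0.82, so coverage is 81% and 87%. For TC−UMC the factor is 0.28 to 0.21. The bias is reweighted and the interval widens, but the cohort shift stays in the estimate.

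**7. Break-even.** Adjusted and unadjusted estimates have equal mean squared error at d = √(SE²adj − SE²unadj)/|factor|. For TC−UMC this is √(0.0741 − 0.0673)/0.304 = 0.27 SD, and the other two contrasts give the same value. With the correlation in step 6 it is 0.29 to 0.35 SD.

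**The case against.** The strongest reply has four parts.

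*The allocation is disclosed.* Section 4.4 gives exact counts by cohort and arm, and the totals in Section 3 agree with them. This stands as far as it goes: a careful reader can reconstruct the design, and the fixed counts imply cohort-specific lists. Section 3 still states a ratio by which nobody is randomised.

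*The model does not ignore cohort.* Section 9.6 iii names cohorts in the correlation structure, gives only a general form, and leaves z open. It is right that the plan does not rule cohort out. But z is not said to contain it, and step 6 shows that the correlation structure does not do its work. The same step does show that 77% coverage is somewhat pessimistic for the planned method: 81% to 87% under the assumed correlations.

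*Nothing in the documents fixes d.* The cohorts share eligibility criteria and a planned instructor, and baseline is adjusted for. A shift of 0.2 SD lies below the break-even, where adding cohort worsens mean squared error. This stands, so the argument for the term is the principle of analysing by the groups within which the trial randomises, not a demonstrated gain. Also, with cohort in the model, the five arm-by-cohort groups leave one between-group degree of freedom (five groups, less the intercept, two arm terms and cohort).

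*The analyses are preliminary.* Section 3 disclaims effectiveness hypotheses, the feasibility outcomes do not use this model, and no readable text says the full-scale trial would change its allocation between cohorts. This limits the severity. It does not justify a wrong design statement or a pooled AC contrast that is mostly non-concurrent.

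**Conclusion.** The concern holds. The 8:3:5 ratio is a pooled total presented as the randomisation ratio; the trial randomises 1:1 and then 4:3:1. The stated model does not analyse by those groups. The allocation facts are certain.

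The statistical impact is conditional on an unknown cohort shift. For an assumed 0.2 to 0.5 SD, only AC against UMC is strongly affected: its bias is about half of one unadjusted standard error at 0.2 SD and 1.2 standard errors at 0.5 SD. TC against UMC is affected little. These figures rest on one time point, equal variances, independent observations and no dropout.

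No stated go/no-go decision depends on these contrasts, so this should be fixed but does not threaten the trial's feasibility aims.

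**What to change.** 1. **Section 3.** Replace the single ratio with 1:1 (TC:UMC) in cohort 1 and 4:3:1 (TC:AC:UMC) in cohort 2, 39:15:24 overall, and say that each cohort has its own block list. Reconcile the cohorts of 32 in Sections 3 and 4.4 with the 38 and 40 in the Precis, and the references to two groups in Sections 4.4 and 9.2 with the arms open in each cohort.
2. **Section 9.6 iii.** Add cohort as a fixed effect in the mean model as the main preliminary analysis, and carry the model into the SAP. State the level at which the GEE clusters, because five arm-by-cohort groups are too few to rely on for between-group variance.
3. **Supportive analysis.** Show the AC contrasts from cohort 2 alone. They avoid the assumption, built into the additive cohort term, that the TC−UMC difference is the same in both cohorts.
4. **Optional.** Tabulate follow-up rates by arm within cohort, descriptively.

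The cost is wording and one model parameter, with the loss of information shown above: 9%, 30% and 16% for TC−UMC, AC−UMC and TC−AC. The cohort 2 contrasts lose more (59% for AC−UMC, 1 − 3.75/9.23; 21% for TC−AC, 1 − 8.57/10.83), which is why they should be supportive only. Sample size, visits and interventions are unchanged.
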